Ruxolitinib cream has shown efficacy in AD and vitiligo. Ruxolitinib cream has shown statistically significant and clinically meaningful efficacy in 2 pivotal Phase 3 studies (INCB 18424-303 and -304) in adults and adolescents with mild to moderate AD and 3% to 20% affected BSA (excluding the scalp). In both AD Phase 3 studies, over 50% (53.8 and 51.3%) of participants (\geq 12 years of age) who applied ruxolitinib 1.5% cream BID for 8 weeks achieved an IGA-TS (ie, IGA score of 0 or 1 with \geq 2-point improvement from baseline) compared with 15.1% and 7.9% of participants who applied vehicle cream, respectively. Participants who applied ruxolitinib cream also saw a substantial improvement in itch (4-point reduction in Itch NRS) compared with participants who applied vehicle in both studies (50.7% and 52.2% for ruxolitinib cream vs 16.3% and 15.4% for vehicle, respectively). In addition, ruxolitinib 1.5% cream administered BID was safe and well tolerated in adolescent and adult participants with AD.

Ruxolitinib cream 1.5% has demonstrated efficacy in vitiligo. Studies INCB 18424-306 and -307 were identically designed randomized, VC, Phase 3 studies in adolescent and adult participants (\geq 12 years old, \approx 10% of whom were adolescents) with vitiligo. Participants received blinded study treatment for 24 weeks and were then offered the opportunity to receive an additional 28 weeks of treatment with ruxolitinib 1.5% cream BID. Both studies met the primary endpoint (p < 0.0001), demonstrating that significantly more participants treated with ruxolitinib 1.5% cream BID achieved a \geq 75% improvement from baseline in the Facial Vitiligo Area Scoring Index at Week 24 compared to participants treated with a vehicle control.

Ruxolitinib 1.5% cream is approved in the US as Opzelura[™] for 1) the topical short-term and noncontinuous chronic treatment of mild to moderate AD in nonimmunocompromised patients 12 years of age and older whose disease is not adequately controlled with topical prescription therapies or when those therapies are not advisable; and 2) the topical treatment of nonsegmental vitiligo in adult and pediatric patients 12 years of age and older. Refer to the Opzelura [™] package insert (Opzelura 2022) for full details.

This study is designed to evaluate the efficacy and safety of ruxolitinib 1.5% cream in participants with LS.

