2.1.1. Scientific Rationale for Study Design

Similar to AD and vitiligo, LS is considered to be an inflammatory dermatosis. Although etiology of LS is unknown, it is considered to be an autoimmune disease with dysregulation of Th1 response. Several cytokines including IL-1, IL-7, IL-15, INF-γ, TNF-α have been implicated in the pathogenesis of LS (Szabo et al 2003, Terlou et al 2012). Additionally, Th1 associated chemokines such as CXCR3 and CCR5, are overexpressed in LS. Similar to AD and vitiligo, JAK1 and JAK2-associated cytokines are involved in the pathogenesis of LS. Ruxolitinib is a selective inhibitor of JAK1 and JAK2 and, based on its demonstrated efficacy in both AD and vitiligo in well-designed pivotal Phase 3 trials, ruxolitinib 1.5% cream is expected to have potential activity in LS.

There is currently no FDA approved treatment of LS. High-potency steroids are the mainstay of treatment; however, their continued use is associated with skin atrophy and other side effects, which limits their use. There are no published studies on topical JAK inhibitors in LS. Prior studies comparing high-potency topical steroids with either topical pimecrolimus (Goldstein et al 2011) or topical tacrolimus (Funaro et al 2014) demonstrate the superiority of high-potency topical steroids. Symptoms (eg, itching or pain) can be partially improved by application of vehicle with up to 75% participants reporting improvement in some studies (Sideri et al 1994). Because of substantial response to vehicle or petroleum ointments, it is crucial to compare ruxolitinib 1.5% cream to vehicle to assess the independent effect of ruxolitinib on LS. For this reason, a random 1:1 allocation design was chosen for this study. Additionally, symptoms of LS may wax and wane and may be exacerbated by sexual or physical activity. Therefore, a 12-week double-blind vehicle-controlled study has been designed, which will allow sufficient length of time to compare ruxolitinib against vehicle and is ethically acceptable. This is in line with prior RCTs in LS, which used a 12-week duration of treatment (Goldstein et al 2011). The proposed study would also assess safety of ruxolitinib 1.5% cream in participants with LS.

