10.4.1. Primary Analysis

The primary analysis will be based on the ITT population. The summary of primary endpoint analysis is provided in Table 10.

Table 10: Summary of Primary Analysis

| Parameter | Definition |
|--------------------------|--|
| Treatment | Ruxolitinib 1.5% cream compared with vehicle cream |
| Population | ITT Population |
| Variable | ITCH4 response at Week 12: ≥ 4-point improvement in Itch NRS score from baseline to at Week 12 |
| Population-level summary | ITCH4 response rate difference with 95% CI |

Note: Participants with missing Week 12 data, as well as all participants who discontinue study treatment at any time before the timepoint of interest, or discontinue from the study for any reason, will be defined as nonresponders. No rescue therapy or treatment switch is allowed in this study.

The primary alternative hypothesis (superiority of ruxolitinib 1.5% cream BID compared with vehicle) against null hypothesis will be tested at a 2 sided $\alpha = 0.05$ level using a Chi-squared test. The p-value and ITCH4 response rate difference with 95% CI will be provided. A Fisher's exact test will be performed for the comparison if either of the treatment groups has an expected cell count less than 5. Summary of ITCH4 rates will be reported for each treatment group. Subgroup analysis by baseline characteristic (eg, IGA, age) will be performed. Details will be provided in the SAP.

The Itch NRS score at each visit will be determined by averaging the 7 daily Itch NRS scores before the corresponding visit day. If 4 or more daily scores are missing (out of the 7), the Itch NRS score at the visit will be set to missing.

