3.3. Sample Size Considerations

Approximately 60 participants will be randomized 1:1 to ruxolitinib 1.5% cream BID or vehicle cream BID. Due to the lack of data with ruxolitinib cream in LS, the sample size was not calculated based on statistical power calculations, but for demonstration of preliminary findings of clinical response. It is anticipated that a sample size of approximately 60 participants will provide sufficient data to determine whether ruxolitinib 1.5% cream warrants further investigation in LS. Also, the sample size is considered sufficient to provide enough data for the evaluation of the ruxolitinib 1.5% cream safety profile in LS.

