7.3. Analysis of the Primary Efficacy Parameter

7.3.1. Primary Efficacy Analysis

The primary efficacy analysis will be based on the ITT population. The primary efficacy endpoint is the ITCH4 response, defined as a \geq 4-point improvement in Itch NRS score from baseline, at Week 12. The comparison of the proportions of participants with ITCH4 at Week 12 will be made between the ruxolitinib 1.5% cream BID arm and the vehicle cream BID arm. The primary hypothesis (the superiority of ruxolitinib 1.5% cream BID compared with vehicle cream in participants with LS) will be tested using a Chi-squared test at a 2-sided $\alpha=0.05$ level; the p-value will be provided. The Wald 95% CI will be provided for the ITCH4 response rate. A Fisher's exact test will be performed for the comparison if either of the treatment groups has an expected cell count less than 5. Summary of ITCH4 rates will be reported for each treatment group.

All nonresponders in the DBVC period, as well as all participants who are missing Week 12 values, will be defined as nonresponders for the primary analysis.

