11.1. Changes to Protocol-Defined Analyses

Not applicable.

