3.2.16.x	Summary of Treatment-Emergent Adverse Events Leading to Discontinuation of Study Drug by MedDRA System Organ Class and Preferred Term	Safety	X
3.2.17.x	Summary of Application Site Reactions by MedDRA Preferred Term in Decreasing Order of Frequency	Safety	X
3.3 Labora	tory		
3.3.1.1.x	Summary of Laboratory Values – Hematology	Safety	X
3.3.1.2.x	Summary of Laboratory Values – Chemistry	Safety	X
3.3.2.1.x	Shift Summary of Hematology Laboratory Values – to the Worst Abnormal Value	Safety	X
3.3.2.2.x	Shift Summary of Chemistry Laboratory Values – to the Worst Abnormal Value	Safety	X
3.3.3.1x	Shift Summary of Hematology Laboratory Values in CTCAE Grade – to the Worst Grade Abnormal Value	Safety	X
3.3.3.2.x	Shift Summary of Chemistry Laboratory Values in CTCAE Grade – to the Worst Grade Abnormal Value	Safety	X
3.4 Vital Si	gns		
3.4.1.x	Summary of Systolic Blood Pressure	Safety	X
3.4.2.x	Summary of Diastolic Blood Pressure	Safety	X
3.4.3.x	Summary of Pulse	Safety	X
3.4.4.x	Summary of Respiratory Rate	Safety	X
3.4.5.x	Summary of Body Temperature	Safety	X

Note: For AE tables ending with "x," separate tables will be provided for the DBVC period, OLE period, and the treatment periods (ie, DBVC and OLE periods). For laboratory and vital sign tables ending with "x," separate tables will be provided for the DBVC and the OLE periods.

Figures

Figure No.	Title	Population
Efficacy		
4.1.1.1	Proportion of Participants Achieving ITCH4 in Treatment Periods	ITT
4.1.1.2	Proportion of Participants Achieving ITCH4 by Baseline ITCH NRS Score in Treatment Periods	ITT
4.1.1.3	Proportion of Participants Achieving ITCH4 by Baseline IGA Score in Treatment Periods	ITT
4.1.1.4	Proportion of Participants Achieving ITCH4 by Baseline Age Group in Treatment Periods	ITT
4.1.1.5	Proportion of Participants Achieving ITCH4 by Baseline Duration of Disease in Treatment Periods	ITT
4.1.1.6	Proportion of Participants Achieving ITCH4 by Pre and Postmenopausal Status in Treatment Periods	ITT
4.1.1.7	Forest Plot of Response Rate Difference in Achieving ITCH4 at Week 12	ITT
4.1.2.1	Mean and Standard Error Plot of By-Visit Itch NRS Score in Treatment Periods	ITT
4.1.2.2	Mean and Standard Error Plot of Change From Baseline in By-Visit Itch NRS Score in Treatment Periods	ITT

Figure No.	Title	Population
4.1.3.1	Mean and Standard Error Plot of Daily Itch NRS Score From Day 1 to Day 28	ITT

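### The SAP attaches its 95% CI for the primary endpoint to the ITCH4 response rate instead of the rate difference the protocol requires, and the Wald method it names is slightly weak for a difference at about 30 per arm

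*SAP*

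**What the plan says.** Protocol 10.4.1 gives the comparison between arms as the primary result: "The p-value and ITCH4 response rate difference with 95% CI will be provided". Table 10 in the same section lists the rate difference with its 95% CI as the population-level summary. The protocol does not name an interval method.

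SAP 7.3.1 follows the same order: test, p-value, interval, Fisher fallback, per-arm summary. Where the protocol has the interval for the difference, the SAP has "The Wald 95% CI will be provided for the ITCH4 response rate". Per-arm rates are covered separately, in a sentence worded the same in both documents: "Summary of ITCH4 rates will be reported for each treatment group". SAP 7.3.1 does not mention the difference.

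Two other places in the SAP bear on the reading. Section 11.1, "Changes to Protocol-Defined Analyses", is marked as not applicable. Appendix A still plans Figure 4.1.1.7, "Forest Plot of Response Rate Difference in Achieving ITCH4 at Week 12". No section names an interval method for the difference.

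**The concern.** Read literally, the SAP does not ask for the interval that the protocol defines as the primary effect summary, and it ties its only named method to a different quantity. A programmer working from SAP 7.3.1 alone could produce two single-arm intervals and no interval for the treatment effect.

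If the difference was meant, the choice of Wald is open to question with arms this small. The unpooled Wald interval tends to be slightly too short, and it uses a different standard error from the planned chi-squared test, so the two can disagree. The sample size was not based on power (SAP 3.3), so much of what readers learn will come from the estimate and its interval. An interval that excludes 0 printed beside a non-significant primary p-value would invite selective reading.

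**Working it through.** **Which quantity was meant.** Three points favour a dropped word over a deliberate change: SAP 11.1 declares no change, the per-arm rates have their own sentence, and Figure 4.1.1.7 needs the difference. A version gap does not explain it. The SAP cites Protocol Amendment 2, and the log for Amendment 3 lists only Section 8.5.3.

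**Inputs.**
- SAP 3.3: "Approximately 60 participants will be randomized 1:1 to ruxolitinib 1.5% cream BID or vehicle cream BID", so 30 per arm.
- Two-sided alpha 0.05. Chi-squared test (taken as uncorrected), or Fisher's exact test if an expected count is below 5.
- True rates in lichen sclerosus are unknown, so they are assumed over ranges. One anchor is the atopic dermatitis itch result in Protocol 2.1: "50.7% and 52.2% for ruxolitinib cream vs 16.3% and 15.4% for vehicle, respectively". A second set uses high vehicle response, because Protocol 2.1.1 expects it ("Because of substantial response to vehicle or petroleum ointments"). The 75% quoted there is symptom improvement, not ITCH4.

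The plan gives no coverage or power figure to reproduce.

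**Formulas**, with d = p1 − p2 and n per arm:
- Wald: d ± 1.96 × √[p1(1−p1)/n + p2(1−p2)/n].
- Newcombe, with Wilson limits (l1, u1) and (l2, u2): lower d − √[(p1−l1)² + (u2−p2)²], upper d + √[(u1−p1)² + (p2−l2)²].
- Chi-squared: z = d / √[2p̄(1−p̄)/n], where p̄ is the pooled rate.

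**One table, 13/30 vs 6/30.** d = 0.4333 − 0.2000 = 0.2333.
- Test: p̄ = 19/60 = 0.3167; variance = 0.3167 × 0.6833 × 2/30 = 0.01443; z = 0.2333/0.1201 = 1.943; p = 0.052. The smallest expected count is 9.5, so chi-squared applies.
- Wald: variance = 0.008185 + 0.005333 = 0.01352; SE = 0.1163; interval 0.2333 ± 0.2279 = +0.5 to +46.1 points. It excludes 0.
- Newcombe: Wilson limits 0.2738 to 0.6080 and 0.0951 to 0.3731. Lower = 0.2333 − √(0.1596² + 0.1731²) = −0.2 points. Upper = 0.2333 + √(0.1747² + 0.1049²) = +43.7 points. It includes 0, in agreement with the test.

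The cause is general. With equal arms the Wald variance equals the test variance minus d²/(2n). Here 0.01443 − 0.05444/60 = 0.01352.

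**All 31 × 31 = 961 tables at 30/30**, weighted by exact binomial probabilities for coverage (5-point grids):

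| | Wald | Newcombe |
|---|---|---|
| Median coverage, 81 scenarios (vehicle 10–50%, difference 0–40 points) | 94.0% (93.1–94.9) | 94.9% (94.0–97.4) |
| Median coverage, 30 scenarios (vehicle 50–75%, difference 0–20 points) | 94.0% (93.1–94.8) | 95.0% (94.2–95.9) |
| Tables where CI excludes 0 but planned p > 0.05 | 24 (8 chi-squared, 16 Fisher) | 8 (all Fisher) |
| Reverse conflicts | 0 | 0 |

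**Probability that the interval excludes 0 while p > 0.05**, by assumed true rates:

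| Ruxolitinib vs vehicle | Wald | Newcombe |
|---|---|---|
| 50.7% vs 16.3% | 1.8% | <0.01% |
| 52.2% vs 15.4% | 1.4% | <0.01% |
| 50% vs 30%, and 70% vs 50% | 0.9% | <0.01% |
| 40% vs 20% | 3.1% | 0.03% |
| 30% vs 10% | 7.1% | 1.9% |
| 20% vs 5% | 18.7% | 8.9% |
| 90% vs 75% | 8.3% | 2.8% |
| 95% vs 75% | 15.8% | 7.9% |

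Over the 30 high-vehicle scenarios the median for Wald is 1.2%.

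**Other arm sizes**, conflicting tables, Wald vs Newcombe: 28 vs 8 at 28/28, 29/29 and 30/31; 24 vs 8 at 31/31 and 32/32; 16 vs 4 at 29/31. At 29/31 Newcombe also has 4 reverse tables (it includes 0 with p = 0.048–0.049).

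**Literal reading, one arm of 30.** Exact coverage, Wald vs Wilson: 78.2% vs 93.9% at a true rate of 5%, 80.9% vs 97.4% at 10%, 87.1% vs 95.1% at 16.3%, 94.6% vs 96.4% at 20%, 95.3% vs 93.0% at 30% and at 70%, 95.7% for both at 50%.

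**The case against.** The strongest reply is that this is an editorial slip. The SAP exists to detail the protocol's analyses, declares no departure and plans a figure of the difference, so the difference will be reported. The separate table shells, not available here, may already say so. This limits the consequence, but the operative sentence still names the wrong quantity.

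A second reply is that criticising Wald for a difference assumes the dropped-word reading. That is true. On the literal reading, however, the SAP conflicts with Table 10 and names no method for the difference at all. Either way the sentence needs correcting.

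A third reply is that the gain from Newcombe is small, and much of this stands:
- The median coverage shortfall is about 1 point. Newcombe's largest departure from 95% (2.4 points) exceeds Wald's (1.9 points), although Newcombe's is on the conservative side.
- Of the 24 conflicts, 12 have vehicle ahead.
- The 8 chi-squared conflicts all have p between 0.0521 and 0.0528.
- Much of the Fisher-branch disagreement comes from that test's conservatism. Newcombe keeps 8 of those 16 tables; for example, 5/30 vs 0/30 gives p = 0.052 and a Newcombe interval of +2.0 to +33.6 points.
- The largest conflict probabilities arise at extreme rates that the documents do not predict.

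Not every conflict is a hairline one, though: 6/30 vs 1/30 gives Fisher p = 0.103 with a Wald interval of +1.0 to +32.4 points, while Newcombe gives −0.3 to +34.2.

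Finally, Wilson is not better than Wald in a single arm at every rate; at 30% and 70% Wald is closer to nominal. That affects only the optional advice on per-arm intervals.

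**Conclusion.** The concern holds, and its weight is modest. The mismatch between SAP 7.3.1 and Protocol 10.4.1 is plain from the text. That a word was dropped is an inference, though a well-supported one.

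On that reading, Wald covers about 94% where 95% is claimed and can contradict the planned test: rarely at middling rates, more often when responders or nonresponders are few. The numerical results rest on about 30 per arm, assumed response rates and an uncorrected chi-squared test; the nearby arm sizes checked show the same pattern.

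The primary decision rests on the p-value, and neither document sets a criterion for the interval. The point should be corrected because the interval is the protocol's defined summary of the primary endpoint, but it does not threaten the primary test.

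**What to change.** Replace the Wald sentence in SAP 7.3.1 with: *The difference in ITCH4 response rates at Week 12 (ruxolitinib minus vehicle) will be reported with a two-sided 95% Newcombe score CI.* Use the same method for Figure 4.1.1.7 and say so in its footnote. If single-arm intervals are also wanted, state them separately. Wilson is the safer choice there because of Wald's poor coverage at low rates. If the sponsor prefers Wald for the difference, the minimum correction is to insert the missing word so that the quantity is right.

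The cost is one sentence and one footnote, with no change to data, test or alpha. Newcombe's mean width is larger than Wald's in 10 of the 81 scenarios, by at most 0.041 (0.334 vs 0.293 at 10% vs 10%), and smaller in the other 71 (0.424 vs 0.437 at 50.7% vs 16.3%). It will not remove every disagreement with Fisher's test, and with unequal arms such as 29/31 it can just include 0 when p is just under 0.05.

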7.3.2. Subgroup Analyses for Primary Endpoint

Subgroups will be formed based on the following participant characteristics and baseline variables for those participants whose data are available:

- Baseline Itch NRS score: ≥ 4 and ≤ 7 versus ≥ 7
- Baseline IGA score: 2, mild; 3, moderate; and 4, severe
- Baseline categorical age: ≥ 18 and ≤ 65 versus ≥ 65
- Baseline duration of disease: $\leq 1, > 1$ and $\leq 5, > 5$
- Childbearing potential: pre versus postmenopausal status

The primary efficacy endpoint will be summarized using descriptive statistics based on the ITT population for the above defined subgroups.

7.4. Analysis of the Secondary Efficacy Parameters

All secondary efficacy analyses will be conducted for the ITT population.

7.4.1. Continuous Efficacy Endpoints

Summary statistics for the following continuous measurements, including change and percentage change from baseline, if applicable, will be presented for each treatment arm:

[figure not shown]
- CLISSCO (total and subscores) at Week 12
- Skin Pain by-visit NRS score at Week 12

The summary statistics includes sample size, mean, median, standard deviation, minimum, maximum, first quartile, third quartile, and 95% CI. An MMRM may be fit for the comparison between ruxolitinib 1.5% cream BID and vehicle cream BID at Week 12. The MMRM will include the fixed effect of treatment, visit, and treatment by visit interaction. The variance-covariance matrix of the within-participant errors in MMRM will be modeled as unstructured.

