10.4.2. Secondary Analyses

All secondary efficacy variables will be summarized using descriptive statistics. For categorical measurements, summary statistics will include sample size, frequency, and percentages. For continuous measurements, summary statistics will include sample size, mean, median, standard deviation, standard error of the mean, minimum, and maximum. Summary statistics for continuous measures will be provided for baseline, the actual measurements at each visit, and the change and percentage change from baseline at each visit, if applicable. For the time to achieve ITCH4, a log-rank test will be used for between -treatment group comparisons. The hazard ratio and its 95% CI will be estimated based on the Cox regression model using Efron's method accounting for ties. Kaplan-Meier curves will be presented by treatment groups. The number of participants, number of events, and number of censoring will be summarized by treatment groups. The Kaplan-Meier estimate of median time will be presented with its 95% CI. The 95% CI will be calculated using the method by Brookmeyer and Crowley (1982).

The Skin Pain NRS score at each visit will be determined by averaging the 7 daily Skin Pain NRS scores before the corresponding visit day. If 4 or more daily scores are missing (out of the 7), the Skin Pain NRS score at the visit will be set to missing.

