2.2. Study Objectives and Endpoints

Table 1 presents the objectives and endpoints.

Table 1: Objectives and Endpoints

Objectives	Endpoints			
Primary				
To establish the efficacy of ruxolitinib 1.5% cream BID in participants with LS.	• ITCH4 response (defined as a ≥ 4-point improvement in Itch NRS score from baseline) at Week 12.			
	(Proportion of participants with ITCH4 at Week 12.)			
Secondary				
To further evaluate efficacy of ruxolitinib 1.5% cream BID in participants with LS.	Change from baseline in CLISSCO score at Week 12.			
	Change from baseline in the Skin Pain NRS score at Week 12.			
	Time to achieve ITCH4.			
To evaluate the safety and tolerability of ruxolitinib 1.5% cream BID.	The type, frequency, and severity of AEs, including the changes in vital signs and clinical laboratory blood samples.			

Table 1: Objectives and Endpoints (Continued)

Objectives	Endpoints

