3.1. Randomization

Approximately 60 participants will be randomized 1:1 to either ruxolitinib 1.5% cream or vehicle cream BID.

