6.1.2. Baseline Disease Characteristics

For the ITT and OLE population, the baseline disease characteristics will be summarized by treatment group and will include, but not limited to the following:

- Disease duration (years)
- LS diagnosis confirmed by biopsy (yes/no)
- Anatomic location (vulva/vagina, other anogenital area, other body areas)
- Complications with LS (yes/no)
- Number of flares/episodes of LS in the past year other than current flare
- Clinical manifestations related to LS (% participants with each of the manifestations)
- Prior treatment received for LS (yes/no)
- History of other skin disease (yes/no)
- Family history of LS (yes/no)
- History of skin infection related to LS requiring antibiotic treatment (yes/no)
- Days since onset of current episode of LS flare/activity
- Skin type (Type I/II/III/IV/V/VI)
- Total % BSA affected
- Baseline Itch NRS score
- Baseline total CLISSCO
- Baseline CLISSCO subscores (total score for each section)

- Baseline Skin Pain NRS
- Baseline total LSCA score
- Baseline IGA score

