7.2. Efficacy Measures

7.2.2. Clinical Lichen Sclerosus Score

The CLISSCO is a validated tool to assess disease severity in vulvar LS. Clinical Lichen Sclerosus Score consists of 12 items divided into 3 sections: symptoms (3 items; likely reversible [ie, itch, pain, dysuria]); signs (3 items; possibly reversible [ie, whitening, petechiae/ecchymosis, fissures]); and architectural changes (6 items; irreversible [ie, skin fusion, perianal involvement, etc]). All symptoms, signs, and architectural changes will be rated on a 4-point Likert scale: 0 (absent), 1 (mild), 2 (moderate), and 3 (severe) (Erni et al 2021). The investigator will be asked to document the score of each of the 12 items; the CLISSCO will be calculated by summing the score of each question with a maximum score of 36 and a minimum score of 0. The higher the score, the more severe the disease. Additionally, the total score for each of the 3 sections (ie, symptoms, signs, and architectural changes) will be summarized by summing the scores of the questions in each section. No imputation will be performed for missing values.

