7.2.5.2. Skin Pain Numerical Rating Scale

Participants will be instructed to complete and record the Skin Pain NRS in a diary each evening beginning on the day of screening through Week 24 or treatment discontinuation. Participants will rate their pain, which will include all types of pain (eg, burning, tearing, pulling, stabbing, etc) severity of the LS by selecting a number from 0 (no pain) to 10 (worst imaginable pain) that best describes the worst level of pain they experienced in the past 24 hours.

The participant's baseline Skin Pain NRS score will be determined by averaging the 7 daily NRS scores before Day 1 (ie, Days –7 to –1) for all the by-visit summaries. The by-visit Skin Pain NRS score for postbaseline visits will be determined by averaging the 7 daily NRS scores before the visit day. If 4 or more daily scores (out of the 7) are missing, the Skin Pain NRS score at the visit will be set to missing. For all daily skin pain-related analyses, baseline will be defined as the last available Skin Pain NRS score during the week prior to Day 1 (ie, Days –7 to –1). No imputation will be performed for missing values.

l
1
Ī
_

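### The MMRM for CLISSCO and Skin Pain NRS omits the baseline score and does not name its response, so the Week 12 contrast is generally less precise than the collected data allow

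*SAP*

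**What the plan says.** SAP 2.2 defines both continuous secondary endpoints as changes, for example "Change from baseline in CLISSCO score at Week 12"; Skin Pain NRS is worded in the same way. SAP 7.4.1 plans summary statistics for them and then adds: "An MMRM may be fit for the comparison between ruxolitinib 1.5% cream BID and vehicle cream BID at Week 12". The model is given as: "The MMRM will include the fixed effect of treatment, visit, and treatment by visit interaction", with an unstructured within-participant covariance. No baseline term is listed there or elsewhere in the available text. The MMRM sentences do not say whether the response is the score, the change or the percentage change, all of which the section mentions for the summaries.

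The baseline values exist. SAP 6.1.2 lists "Baseline total CLISSCO" and the subscores among the baseline characteristics. SAP 7.2.5.2 states that the "baseline Skin Pain NRS score will be determined by averaging the 7 daily NRS scores before Day 1".

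On design, SAP 3.1 says "Approximately 60 participants will be randomized 1:1 to either ruxolitinib 1.5% cream or vehicle cream BID"; neither document specifies stratification. Protocol 10.4.2 does not mention an MMRM: "All secondary efficacy variables will be summarized using descriptive statistics".

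**The concern.** With about 30 participants per arm and no stratification, the arms can differ at baseline by chance. Neither possible response handles this well without a baseline covariate. A change score subtracts the baseline with a slope fixed at 1, which over-corrects when the true slope is below 1. A raw score ignores the baseline altogether. In both cases the model leaves variation in the error term that the baseline could explain.

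At stake is the precision of the only between-arm model that the available text specifies for these two endpoints, in a trial whose stated purpose (SAP 3.3) is to judge whether the cream merits further study. The unnamed response adds a second problem. SAP 10 has the sponsor unblinded after the primary lock, so as written the response could be chosen at that point, and the two choices can have quite different standard errors.

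**Working it through.** The plan states no SD, effect size or precision target for these endpoints, and SAP 3.3 says that the sample size is not power-based. There is therefore no figure to reproduce.

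**Inputs.** N = 60, 30 per arm (SAP 3.1). Fixed effects and unstructured covariance from SAP 7.4.1. Assumed, because the documents do not give them: the baseline-to-Week-12 correlation r (shown over a range), equal SDs at the two times, and a common linear slope in both arms.

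**Formulas.** With complete data, an unstructured MMRM with treatment-by-visit gives the ordinary difference in Week 12 means. Adding baseline and baseline-by-visit gives the ANCOVA contrast. In SD² units the per-arm variances are:

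- change score: 2(1 − r)
- raw score: 1
- baseline-adjusted: (1 − r²) × (N − 3)/(N − 4) = (1 − r²) × 57/56, where 57/56 = 1.0179 is the cost of estimating the slope.

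The adjusted-to-planned variance ratio is therefore (1 + r)/2 × 1.0179 for a change response and (1 − r²) × 1.0179 for a raw response. For example, at r = 0.5 the change ratio is 0.75 × 1.0179 = 0.763, and the interval is 1 − √0.763 = 12.6% narrower.

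**Chance imbalance.** The SD of the baseline mean difference is √(2/30) = 0.258 baseline SD. An imbalance d shifts the change-score contrast by −(1 − r)d and the raw-score contrast by +r·d. The shifts below use d = 0.258.

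| r | Change: variance ratio | Change: CI narrower | Change: N needed without baseline to match 60 | Raw: variance ratio | Shift, change (SD) | Shift, raw (SD) |
|---|---|---|---|---|---|---|
| 0.3 | 0.66 | 18.7% | 90.7 | 0.93 | −0.18 | +0.08 |
| 0.5 | 0.76 | 12.6% | 78.6 | 0.76 | −0.13 | +0.13 |
| 0.7 | 0.87 | 7.0% | 69.3 | 0.52 | −0.08 | +0.18 |
| 0.8 | 0.92 | 4.3% | 65.5 | 0.37 | −0.05 | +0.21 |
| 0.9 | 0.97 | 1.7% | 62.0 | 0.19 | −0.03 | +0.23 |

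**Break-even.** The gain disappears when r exceeds 2/1.0179 − 1 = 0.96 (change), or falls below √(1 − 1/1.0179) = 0.13 (raw).

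**Checks.** Simulation of 40,000 trials per r with complete data gave change ratios of 0.665, 0.768, 0.864, 0.917 and 0.964 and raw ratios of 0.930, 0.768, 0.525, 0.365 and 0.193. The mean unadjusted change contrast was within 0.002 of zero, which confirms no bias. Given a +1-SD imbalance, the adjusted estimate stayed within 0.01 of zero. With four post-baseline visits, an assumed 15% monotone dropout and a known covariance, the planned-to-adjusted SE ratios at r = 0.3, 0.5 and 0.7 were 1.23, 1.14 and 1.08 (change) and 1.05, 1.14 and 1.37 (raw). Dropout of that size therefore does not alter the picture.

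**Unnamed response.** At r = 0.7 the SE of the planned contrast is 0.258 SD for a raw score and √(2 × 0.3) × 0.258 = 0.200 SD for a change score.

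**The case against.** The strongest case is that nothing here is invalid and little depends on it. The MMRM is optional, the Protocol treats these endpoints descriptively, alpha is assigned only to the primary analysis, and the trial was not sized for precision. All of that stands.

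Second, change is the natural reading because the endpoints are defined as changes, so the large raw-score figures describe a less likely model. This is also fair; the change-score columns carry the main message. Under that reading the gain may be small for total CLISSCO, because the SAP describes half of the 12 items as fixed: "architectural changes (6 items; irreversible". A high r is then plausible. The point is weaker for the symptom and sign subscores, which the SAP calls likely or possibly reversible, and it does not apply to Skin Pain NRS.

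Third, equal SDs are an assumption. Let k be the Week 12 SD divided by the baseline SD. The change-score variance becomes 1 + k² − 2rk and the adjusted variance k²(1 − r²) × 57/56. At k = 1.25 the ratio is 0.811/0.8125 = 0.998 at r = 0.7 and 0.5725/0.5625 = 1.018 at r = 0.8: no gain, or a loss of about 2%. At k = 0.8 and r = 0.7 it is 0.332/0.52 = 0.64, a larger gain. The size is thus conditional on k as well as r. The most that adjustment can cost relative to a change-score model is the slope factor, about 2% of the variance, so the recommendation survives. A floor in Skin Pain NRS would strain both the equal-variance and the linear-slope assumptions.

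Finally, the table shells are in a separate document and may name the response. That could settle the second gap, but it would not change the explicit list of fixed effects.

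**Conclusion.** The concern holds. The specified model omits a baseline covariate that is already collected, and the text does not name the response. The loss is one of efficiency and of correction for the imbalance that actually occurs. It is not a loss of validity: the contrast is unbiased over randomization with complete data, type I error is not inflated, and the ITCH4 analysis is untouched.

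Under the natural change-score reading with equal SDs, the confidence interval is wider than it need be by an amount that adjustment would recover: 18.7% of its width at r = 0.3, falling to 1.7% at r = 0.9. The gain is likely to be at the low end for total CLISSCO. Under a raw-score reading the loss grows with r instead. These sizes rest on an assumed r and SD ratio. The change should be made because it is nearly free, not because the planned analysis is wrong.

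**What to change.** Amend SAP 7.4.1 along these lines:

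> The MMRM response is change from baseline at each post-baseline DBVC visit (Weeks 2, 4, 8 and 12). Fixed effects are treatment, visit, treatment-by-visit interaction, baseline score and baseline-by-visit interaction, with unstructured covariance. For Skin Pain NRS the baseline covariate is the 7-day average defined in Section 7.2.5.2. For each CLISSCO subscore it is the baseline value of that subscore.

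The optional wording should also become a firm statement that the model will be fitted; otherwise the amendment may have no effect. With baseline and baseline-by-visit in the model, the treatment contrast is the same whether score or change is the response, so the fix also removes that ambiguity.

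The cost is a few sentences and four fixed-effect parameters (one baseline slope per visit). No new data are needed. No participant is lost, because one without a baseline already has no change score.
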